Anastomotic Leakage in Colorectal Cancer Surgery in Syria: Risk Factors and Improvements Following Guideline Implementation – A Retrospective Cohort Study

November/16/2025

NCT07092631

**Study Protocol: Follow-Up Cohort on Anastomotic Leakage in
Colorectal Cancer Surgery at Damascus Hospital, Syria**

Study Title:

Official Title:

Anastomotic Leakage in Colorectal Cancer Surgery in Syria: A Retrospective Cohort
Study Before and After Guideline Implementation

Brief Title:

Anastomotic Leakage in Colorectal Cancer Surgery, Syria

Study Design:

- Type: Observational, Retrospective Cohort Study
- Number of Cohorts: Two sequential cohorts
- The first cohort: Pre-guideline cohort (January 2016 – March 2024)
- The follow-up cohort: Post-guideline follow-up cohort (April 2024 – October 2025)
- Study Phase: N/A (observational)
- Number of Participants: 19 (follow-up cohort)

Study Objectives:

- Primary Objective:

1. To evaluate the incidence of anastomotic leakage (AL) after implementation of updated institutional guidelines for colorectal cancer surgery.
- Secondary Objectives:
 1. To assess postoperative complications, perioperative blood transfusions, ICU admissions, and postoperative mortality in the follow-up cohort.
 2. To compare outcomes with the pre-guideline cohort to determine the impact of guideline implementation.
 3. To evaluate the effectiveness of perioperative interventions targeting modifiable risk factors (e.g., hypoalbuminemia, transfusions, steroid use)

Study Setting:

Department of General Surgery, Damascus Hospital, Syria.

Resource-limited, conflict-affected environment with predominantly open surgery; laparoscopic surgery available for selected patients.

Eligibility Criteria:

- Inclusion Criteria:

Patients who underwent elective resection of the sigmoid colon or rectum for histologically confirmed colorectal adenocarcinoma between April 2024 and October 2025.

Availability of complete medical records and laboratory data relevant to the study outcomes.

- Exclusion Criteria:

Emergency surgeries or non-elective resections.

Non-neoplastic (non-tumor) resections.

Incomplete or missing medical records.

Interventions / Exposure:

- No experimental interventions; retrospective observational study.
- Patients were managed under updated hospital guidelines, which included:

(Preoperative nutritional optimization) albumin ≥ 3.5 g/dL when possible

Reduced perioperative blood transfusions

Enhanced intraoperative safety protocols

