Postoperative monitoring for high-risk patients

Outcome Measures:

- Primary Outcome:

Anastomotic leakage (AL), defined according to ISREC criteria: a defect in the intestinal wall at the colorectal or colo-anal anastomosis causing communication between intra- and extraluminal compartments. Confirmed clinically or radiologically.

- Secondary Outcomes:

Postoperative complications

ICU admission

Perioperative blood transfusions

Postoperative mortality

Data Collection:

Retrospective extraction from patient charts, operative notes, laboratory results, and radiology reports.

Structured follow-up telephone interviews where applicable.

Collected variables: demographics, lifestyle factors, comorbidities, tumor characteristics, surgical details, laboratory data, and postoperative outcomes.

Statistical Analysis:

Descriptive statistics for baseline characteristics.

Comparisons with pre-guideline cohort using Chi-square or Fisher's exact test for categorical variables; t-test or Mann-Whitney U test for continuous variables.

Statistical significance: $p < 0.05$.

Analysis performed using SPSS version 24.

Ethical Considerations:

Ethical approval obtained from the Institutional Review Board of the Syrian Private University (IRB No. 1497/436.)

Retrospective nature: waiver of informed consent obtained where applicable.

Patient confidentiality maintained via anonymization and secure data storage.

Timeline:

- Study Start Date January 2016 (original cohort)
- Follow-up Cohort Data Collection Start April 2024
- Follow-up Cohort Data Collection End October 2025
- Study Completion Date October 2025

Study Significance:

This follow-up cohort evaluates the real-world impact of evidence-based guideline modifications on anastomotic leakage and other postoperative outcomes in a resource-limited, war-affected setting. The findings will inform future clinical practice and risk-reduction strategies for colorectal surgery in similar low-resource contexts.

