### **Postoperative Data:**

- Post-operative ICU.
- Post-operative Complications.
- Ileostomy.
- Steroids use.
- Serum Albumin level.
- Occurrence of anastomotic leakage
- Patient Final status.

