### **Statistical Analysis:**

All collected data was entered into a secure, password-protected database. Descriptive statistics were used to summarize patient demographics, tumor characteristics, and surgical variables. Categorical variables were presented as frequencies and percentages, while continuous variables were reported as means with standard deviations or medians with interquartile ranges, as appropriate.

Univariate analyses was performed to evaluate the association between each potential risk factor and the occurrence of anastomotic leakage within 30 days postoperatively.

Statistical analysis was conducted using SPSS software, version 26 (IBM Corp., Armonk, NY, USA). A p-value < 0.05 was considered statistically significant. Data validation and quality control procedures were applied throughout the analysis to ensure accuracy and consistency.

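### Leak detection may differ between the two eras, so the before/after leak comparison (secondary objective 2) may mix true incidence with detection

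*Protocol*

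**What the plan says.** **Exposure.** Under Interventions / Exposure, the Protocol introduces the package with "Patients were managed under updated hospital guidelines, which included". The last item on that list is "Postoperative monitoring for high-risk patients". Its content and frequency, any use of imaging, and earlier practice are not described.

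**Outcome, follow-up cohort.** The Protocol's primary outcome is "Anastomotic leakage (AL), defined according to ISREC criteria", and a leak is "Confirmed clinically or radiologically". No severity grade, imaging trigger, time window or blinded adjudication is given. The source is "Retrospective extraction from patient charts, operative notes, laboratory results, and radiology reports", with telephone interviews where applicable.

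**Outcome, pre-guideline cohort.** In the Combined protocol and SAP, Postoperative Data lists "Occurrence of anastomotic leakage" with no definition or confirmation rule in the text available. Statistical Analysis refers to "the occurrence of anastomotic leakage within 30 days postoperatively". Variables and Data Collection names patient files, operative reports and follow-up records, plus a questionnaire where applicable. It does not name radiology reports.

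**Use.** Secondary objective 2 of the Protocol is "To compare outcomes with the pre-guideline cohort to determine the impact of guideline implementation". The planned tests are unadjusted (Chi-square or Fisher's exact for categorical variables), with 19 follow-up patients against 100 pre-guideline patients.

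**The concern.** How often a leak is recorded depends on how often it occurs and how often it is looked for. Here one component of the exposure could affect the second. The endpoint admits leaks seen only on imaging, which are the ones most sensitive to looking. The named sources also differ in the same direction.

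Harmonising definition, window and sources is necessary but may not be enough. If closer observation is part of the guideline, a common definition would still pick up small contained defects more often in the era that looks harder. A true fall in leaks could then look smaller or absent, and objective 2 could conclude that the guideline did little. Nothing in the plan would let a reader separate the two explanations.

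**Working it through.** The plan states no leak rate, effect size or power, so there is no figure of its own to reproduce. The sample sizes (100 and 19) come from the documents. **All leak risks, detection probabilities and high-risk shares below are assumptions.**

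**Model.** Observed rate = true rate × detection probability. Hence apparent risk ratio = true risk ratio × (detection after ÷ detection before).

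**1. Detection rises for all leaks, to 100% after.**

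| Detection before | Apparent ratio, no true change | Apparent ratio, true halving |
|---|---|---|
| 90% | 1.00/0.90 = 1.11 | 0.5/0.90 = 0.56 |
| 80% | 1.00/0.80 = 1.25 | 0.5/0.80 = 0.625 |
| 70% | 1.00/0.70 = 1.43 | 0.5/0.70 = 0.71 |
| 50% | 1.00/0.50 = 2.00 | 0.5/0.50 = 1.00 |

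**2. Detection rises only in high-risk patients, which is closer to the text.** Let h be the share of leaks arising in high-risk patients. Detection is 70% before in everyone, and 90% after in high-risk patients only. Overall detection after = 0.70 + 0.20h.

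| h | Detection after | Ratio, no true change | Ratio, true halving |
|---|---|---|---|
| 0.25 | 0.75 | 0.75/0.70 = 1.07 | 0.54 |
| 0.50 | 0.80 | 0.80/0.70 = 1.14 | 0.57 |
| 1.00 | 0.90 | 0.90/0.70 = 1.29 | 0.64 |

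**3. When would a benefit appear reversed?** Only if the true risk ratio exceeds detection before ÷ detection after. For h = 1 this is 0.70/0.90 = 0.78, so only a true reduction under 22% would be reversed. For h = 0.5 it is 0.70/0.80 = 0.875, a reduction under 12.5%. Reversing a true halving needs detection to more than double.

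**4. Absolute size.** With a true risk of 10% to 15% in both eras and h = 1, observed rates go from 7.0%–10.5% to 9.0%–13.5%. That is 2 to 3 percentage points, or 19 × 0.02 = 0.4 to 19 × 0.03 = 0.6 of a patient. A single leak seen only on imaging moves the follow-up rate by 1/19 = 5.3 points.

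**5. Effect on the planned test.** The probability of p < 0.05 is the sum, over all leak counts a of 100 and b of 19, of the two binomial probabilities wherever two-sided Fisher gives p < 0.05. The documents do not state sidedness; two-sided is assumed. For a true fall from 20% to 10%:

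- equal detection: 10.3%
- 80% before, 100% after: 3.7%
- 70% before, 100% after: 2.0%

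Power is very low even without the bias. As a yardstick for precision, 2 leaks in 19 has an exact 95% interval of 1.3% to 33.1%.

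**The case against.** The strongest reply is that the mechanism is not documented. A reader might infer that the guideline intensified monitoring, that monitored patients were imaged more, and that contained defects went unimaged before. No passage says so. Monitoring could mean vital signs or closer ward observation, and neither document describes imaging practice in either era. Patient files in the pre-guideline cohort may also have contained radiology reports. This stands: the documents support saying that detection may differ, not that it did.

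A second reply is that the posited bias works against the guideline and could not by itself create a false improvement, and that a reversal needs a modest true effect or a large detection change (step 3). This stands too.

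A third is that imprecision swamps the bias in 19 patients. That is true of the size in step 4. But imprecision shows in the confidence interval, whereas a detection shift does not.

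A fourth concerns the tempting remedy of replacing the comparison endpoint with any leak that was treated. A leak found only through closer observation and then treated would still count, while the same leak undetected earlier would not, and events would be lost. This argues for an added sensitivity analysis limited to reoperation or drainage, with the main endpoint kept. Even that is less dependent on detection rather than free of it, since drainage can follow an imaging finding.

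**Conclusion.** The concern holds as a risk that the plan does not address, confined to secondary objective 2. Three features of the text support it: monitoring of high-risk patients belongs to the exposure, radiological confirmation alone suffices, and radiology reports are a named source in one cohort only. If detection rose, the bias would mask or shrink a reduction. Its size is unknown. Under the assumptions above, a true halving would appear as a ratio between 0.54 and 0.71, reaching 1.00 only if detection doubled from 50% to 100%.

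A reader might go further and conclude that the primary result is biased. It is not on this ground: the primary objective is leak incidence in the follow-up cohort, and the descriptive estimate in the 19 stands under its own definition. Nor do the documents show that an observed reduction would be an artefact of detection; this mechanism points the other way.

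**What to change.** - Keep any ISREC leak as the before/after endpoint, with one definition, one time window and one set of sources applied to both cohorts.
- Add a pre-stated sensitivity comparison restricted to leaks that led to reoperation or drainage, abstracted the same way from charts and operative reports in both cohorts.
- Report leaks by cohort and mode of detection (clinical, or radiology only), with the number of patients who had postoperative imaging of the anastomosis where records allow.
- State that a change in leak rate, or its absence, will not be attributed to the guideline unless the two analyses agree. Judge agreement on estimates and intervals, since neither test has useful power. Agreement deals with detection only, not with other differences between eras.
- Leave the descriptive incidence in the 19 as it is.

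**Cost.** One extra coded field for leak cases, and a check for imaging in up to 100 + 19 = 119 records, which may require retrieving pre-guideline radiology reports. The sensitivity comparison will have few events and should be presented as such.

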## Background:

Anastomotic leakage (AL) is one of the most serious complications following colorectal surgery, associated with increased morbidity, mortality, prolonged hospital stays. It occurs when there is a disruption at the surgical connection between two segments of the bowel, most commonly involving the colon or rectum. Despite advances in surgical techniques and perioperative care, AL remains a persistent concern, particularly in colorectal cancer patients undergoing resection.

This study was conducted in Damascus, Syria—a country that has endured over a decade of armed conflict, leading to profound disruptions in the healthcare system. Hospitals in such settings face ongoing shortages of medical supplies and limited access to updated surgical technologies. Laparoscopic surgery is not routinely available, and open surgery continues to be the standard approach for most colorectal procedures, including elective cases. Given these challenges, there is a critical need for context-specific data to guide clinical decision-making and improve patient outcomes.

The present study aims to identify the risk factors associated with anastomotic leakage among colorectal cancer patients who underwent surgery in a resource-limited, conflict-affected setting. Understanding these factors can contribute to safer surgical practice and more informed perioperative management in similar environments worldwide.

## Objective:

To identify clinical, demographic, surgical, and pathological factors associated with an increased risk of anastomotic leakage in patients undergoing surgery for colorectal cancer.

## **Study Design:**

- **Study Type:** Observational
- **Study Design:** Retrospective Cohort Study
- **Time Perspective:** Retrospective
- **Study Period:** January 2016 to February 2024
- **Data Source:** Patients medical records and surgical reports from Damascus Hospital.

## **Study Population:**

### **Inclusion Criteria**

- Patients who underwent colorectal cancer surgery for tumor-related indications.

### **Exclusion Criteria**

- Emergency cases.
- Non-tumor related colorectal surgeries.

## **Primary Outcome Measures:**

Association Between Patient- and Surgery-Related Risk Factors and the Incidence of Anastomotic Leakage.

## **Variables and Data Collection:**

Data was extracted from patient files, operative reports, and follow-up records. Additional follow-up was performed via a structured questionnaire where applicable. Collected variables include:

### **Demographic & Clinical Variables:**

- Age, sex
- Smoking status
- Medical history (diabetes, hypertension)

### **Tumor Characteristics:**

- Tumor Site (Rectum / Sigmoid colon)
- Radiotherapy (in case of rectum mass)
- TNM
- Tumor differentiation grade.

### **Surgical Factors :**

- Type of surgery (open / laparoscopic).
- Peri-operative blood transfusion.
- Closing Method (manual / staplers)
- Surgical Contamination.

### **Postoperative Data:**

- Post-operative ICU.
- Post-operative Complications.
- Ileostomy.
- Steroids use.
- Serum Albumin level.
- Occurrence of anastomotic leakage
- Patient Final status.

### **Sample Size:**

All eligible patients meeting the inclusion criteria within the defined period were included. The final sample size was 100 patients.

### **Statistical Analysis:**

All collected data was entered into a secure, password-protected database. Descriptive statistics were used to summarize patient demographics, tumor characteristics, and surgical variables. Categorical variables were presented as frequencies and percentages, while continuous variables were reported as means with standard deviations or medians with interquartile ranges, as appropriate.

Univariate analyses was performed to evaluate the association between each potential risk factor and the occurrence of anastomotic leakage within 30 days postoperatively.

Statistical analysis was conducted using SPSS software, version 26 (IBM Corp., Armonk, NY, USA). A p-value < 0.05 was considered statistically significant. Data validation and quality control procedures were applied throughout the analysis to ensure accuracy and consistency.

### **Ethical Considerations:**

This study was approved by the IRB of Syrian Private University (IRB No. 1497/436).

Since this is a retrospective cohort study with no direct patient contact and anonymized data, the requirement for informed consent has been waived. Data confidentiality and patient privacy were strictly maintained.

### **Limitations:**

One limitation of this study is the absence of a laparoscopic surgery comparison group, which may limit the generalizability of the findings to settings where minimally invasive techniques are routinely used. However, given the resource-constrained environment in which this study is conducted, the results are expected to provide valuable insights for similar healthcare contexts, particularly in conflict-affected or low-income regions.

### **Timeline:**

**Study Start Date:** Mar/04/2024

**Primary Completion Date:** Apr/08/2024

**Study Completion Date:** Jul/20/2024
